Maintaining Continuous Positive Airway Pressure (CPAP) is a common form of support to patients with respiratory distress admitted to Intensive Care Units (ICU) of industrialized countries. Nasal CPAP (NCPAP) is effective in reducing hypoxemia and contributes to reducing the number of children requiring endo-tracheal intubation and mechanical ventilation. CPAP is most frequently delivered to neonates using conventional mechanical ventilators, which involves much higher costs. There are other ways of delivering CPAP. Bubble-CPAP is a simple, non-invasive delivery system with potential to reduce hypoxemia in neonates with acute respiratory failure. Equipment of bubble CPAP is now available at a fraction of the cost of mechanical ventilators. Bubble-CPAP has several advantages over mechanical ventilation such as lower cost, easier application by nursing staff and lower risk of complications. It therefore has potential as an inexpensive and affordable method of delivering CPAP in developing countries. Moreover, all the necessary equipment could be made locally.

Humidified high flow air / O₂ supplementation has been suggested in case series to be useful in reducing the need for mechanical ventilation in infants with bronchiolitis. However, there have been no randomized trials to compare it with bubble CPAP or with standard O₂ supplementation by nasal prongs. It is simple to apply, but requires careful monitoring and delivers uncertain levels of CPAP.

Hypoxaemia is documented in nearly half of the patients admitted to the ICU of the Dhaka Hospital of ICDDR,B and many of them present with impending respiratory failure. Children under five with severe pneumonia nearly always have associated severe malnutrition, and many receive mechanical ventilation. This is expensive and is associated with high complication and mortality rates – the death rate was 81% among the **26 children under five who were ventilated due to respiratory failure between January and October, 2010**. There are no published data on the use of bubble-CPAP in children, beyond the newborn period, or in the treatment of pneumonia in developing countries, and no controlled trials of CPAP. We propose to conduct a study to compare the efficacy of (a) bubble CPAP with that of (b) the standard O₂ supplementation by nasal prongs and (c) humidified high flow nasal cannula air / O₂ in the management of hypoxic children with respiratory failure admitted to the ICU of the Dhaka Hospital of ICDDR,B.

NOTE: Does the study meet the definition of clinical studies/trials given by the International Committee of Medical Journal Editors (ICMJE)? Yes No

Please note that the ICMJE defined clinical trial as "Any research project that prospectively assigns human subjects to intervention and comparison groups to study the cause-and-effect relationship between a medical intervention and a health outcome".

If YES, after approval of the ERC, the PI should complete and send the relevant form to provide required information about the research protocol to the Committee Coordination Secretariat for registration of the study into websites, preferably at the <https://register.clinicaltrials.gov/>. It may please be noted that the PI would require to provide subsequent updates of the research protocol for updating protocol information in the website.

Targeted Population (Check all that apply):

- No ethnic selection (Bangladeshi)
 Bangalee
 Tribal group

- Expatriates
 Immigrants
 Refugee

Consent Process (Check all that apply):

- Written
 Oral
 None

- Bengali Language
 English Language

Proposed Sample Size:

Sub-group (Name of subgroup (e.g. Men, Women) and Number

Name	Number	Name	Number
(1)	975 (325 in each arms)	(3)	
(2)		(4)	

Total sample size: 975Will the sample(s) be kept for future use? Yes No NA

If yes, how long the samples be preserved?

Will the consent be obtained from the study participants? Yes No NA

What types of tests will be carried out with the preserved samples? _____

Will the samples be shipped to other country(ies)? Yes No NA

If yes, name of institution(s) and country(ies): _____

Will the samples be returned to the Centre? Yes No NA Who will be the custodian of the samples? : NA _Who will be the owner of the samples? : NA _Has an MOU been made for the protocol? Yes No NA If yes, has copy of the MOU been submitted to IRB? Yes No NA **Determination of Risk: Does the Research Involve (Check all that apply):**

- | | |
|---|---|
|  Human exposure to radioactive agents? |  Human exposure to infectious agents? |
|  Foetal tissue or abortus? |  Investigational new drug |
|  Investigational new device?
(specify:) |  Existing data available via public
archives/sources |
|  Existing data available from Co-investigator |  Pathological or diagnostic clinical specimen
only |
| |  Observation of public behaviour |
| |  New treatment regime |

Yes No Is the information recorded in such a manner that study participants can be identified from information provided directly or through identifiers linked to the study participants?

Yes No Does the research deal with sensitive aspects of the study participants' behaviour; sexual behaviour, alcohol use or illegal conduct such as drug use?

Could the information recorded about the individual if it became known outside of the research:

Yes No Place the study participants at risk of criminal or civil liability?

Yes No Damage the study participants' financial standing, reputation or employability, social rejection, lead to stigma, divorce etc.?

Do you consider this research (Check one):

- Greater than minimal risk No more than minimal risk
 Only part of the diagnostic test

Minimal Risk is the risk when the probability and magnitude of the anticipated harm or discomfort in participating in the proposed research are not greater in and of themselves than those ordinarily encountered in daily life or during the performance of routine physical, psychological examinations or tests, e.g. the risk of drawing a small amount of blood from a healthy individual for research purposes is no greater than the risk of doing so as a part of routine physical examination.

Yes/ No

Is the proposal funded?

If yes, sponsor Name: (1) Partially funded (Aus\$40,000) by the Centre for International Child Health, through a Knowledge Generation Grant from AusAID

(2) The University of Melbourne (scholarships): Aus\$22,800/year

Yes/No/NA (if the proposal is already funded, mark NA)

Is the proposal being submitted for funding?

If yes, name of funding agency: (1)

(2)

Do any of the participating investigators and/or member(s) of their immediate families have an equity relationship (e.g. stockholder) with the sponsor of the project or manufacturer and/or owner of the test product or device to be studied or serve as a consultant to any of the above?

IF YES, a written statement of disclosure to be submitted to the Centre's Executive Director.

Dates of Proposed Period of Support

(Day, Month, Year - DD/MM/YY)

Beginning Date : August, 2011

End Date : July, 2013 (or up to desired sample collection)

Appendix 3: Response to External Reviewer’s Comments	
Appendix 4: Abstract Summary covering eight points specified by the ERC.....	
Check-List.....	35

Check here if appendix is included

Project Summary

Briefly describe the hypothesis, objectives, and the relevant background of the project, and also the experimental design and research methods for achieving the objectives. This description will serve as a succinct and precise and accurate description of the proposed research is required. This summary should be stand alone, and be fully understandable and interpretable when removed from the main application.

Principal Investigator: [name]
Research Protocol Title: Use of bubble CPAP compared to nasal prong oxygen or humidified high flow in children under five with severe pneumonia and hypoxaemia: a randomized trial
Total Budget US\$: \$US 1,15,706 Beginning Date : August, 2011 Ending Date: July, 2013 (or up to desired sample collection)

Continuous Positive Airway Pressure (CPAP) is a common form of support for patients admitted to Intensive Care Units (ICUs) of industrialized countries with respiratory distress (1). Nasal CPAP (NCPAP) is effective in correcting hypoxemia and contributes to reducing the number of children requiring endo-tracheal intubation and mechanical ventilation (2). CPAP is most frequently delivered to neonates using conventional mechanical ventilators, and thus there is minimal or no cost saving. There are other ways of delivering CPAP, such as Bubble-CPAP, which requires a source of gas flow (typically 6–8 L/ minute in a neonate), an air-oxygen blender, a humidifier and a T-piece.(3). The expiratory arm is inserted in a bottle of water and the level of CPAP delivered is equivalent to the length of the expiratory tubing that remains under water. Robust equipment is now available at a fraction of the cost of mechanical ventilators. Bubble-CPAP has potential advantages over the mechanical ventilation, such as lower cost, ease of application by nursing staff, lower risk of complications, and has been proposed as an inexpensive method of delivering CPAP in developing countries (3).
 
High flow air/ oxygen mix is useful in reducing the indication of mechanical ventilation (4); however, there is a lack of randomized studies comparing it with bubble CPAP or with standard flow O₂ supplementation by nasal prongs. High flow air/oxygen mix uses flows of 2 litre per kg per minute of blended air / oxygen mix, usually with a low fraction of inspired oxygen (say 25-40%). It is easy to apply, but requires additional equipment to standard oxygen therapy, and closer monitoring. “High flow” delivers uncertain levels of CPAP, so it is not clearly superior to bubble-CPAP, and there have been no controlled comparative trials of these two techniques.
 
Pneumonia and malnutrition are two of the most common co-morbidities in children in developing countries (5). In hospitals in resource-poor settings, children with severe malnutrition and pneumonia often present with respiratory distress with or without severe hypoxaemia and impending respiratory failure (6). They initially receive O₂ supplementation through nasal prong or face mask. Support from bubble CPAP might help to effectively treat hypoxaemia, improve respiratory function, avoid the need for mechanical ventilation and its complications, and reduce mortality.
 
Almost half of the patients admitted in the intensive care unit of the Dhaka hospital of ICDDR,B present with hypoxaemia, many with impending respiratory failure. Children with pneumonia also invariably have severe malnutrition with or without diarrhoea ([name], MMed thesis, unpublished data). They often need mechanical ventilation, with attendant costs, complications and high mortality rates. However, no published data are available about the use of bubble-CPAP in children with pneumonia and malnutrition and there have been no controlled trials of CPAP in developing countries.
 
The main purpose of our proposed study is to compare the efficacy of (a) bubble CPAP with that of (b) the standard O₂ supplementation by nasal prongs and (c) humidified high flow nasal cannula in the management of hypoxic children with respiratory failure admitted to the ICU of the Dhaka Hospital of ICDDR,B.


KEY PERSONNEL (List names of all investigators including PI and their respective specialties)

Name	Professional Discipline/ Specialty	Role in the Project
1. [name]	Paediatric respiratory physician	Principal Investigator
2. [name]	Internist	Co-PI
3. [name]	Medicine specialist/Pulmonologist	Co-PI
4. [name]	Paediatrician Anaesthetist/Intensive care specialist	Co-PI
5. [name]	Paediatrician/Intensive care specialist	Co-PI
6. [name]	Paediatrician	Co-PI
7. [name]	Nutritionist and Epidemiologist	Co-I
8. [name]	Internist/Paediatrician	Co-I
9. [name]	Internist	Co-I

Description of the Research Project

Hypothesis to be Tested:

Please briefly list the Hypothesis to be tested and provide the scientific basis of the hypothesis, critically examining the observations leading to the formulation of the hypothesis.

On the basis of the above background, our primary hypothesis is that:

1. In children with severe pneumonia and hypoxaemia the probability of treatment failure (see definition below) will be significantly lower when respiratory support is initially provided by bubble-CPAP compared to standard nasal prong O₂ and humidified high flow for children with severe pneumonia and hypoxaemia.

Our secondary outcomes are:

2. Mortality rate at hospital discharge, rate of need for mechanical ventilation, rates of nosocomial infections (if clinical features of new episode of infection develops 48-72 hours after admission to a hospital), rates of multi-organ failure at 7 days, length of hospital stay, rate of absconding, bacterial aetiology and rates of isolation of TB will be significantly different when treatment is provided by bubble-CPAP, compared to standard nasal prong O₂ and humidified high flow for children with severe pneumonia and hypoxaemia

Specific Aims:

Describe the specific aims of the proposed study. State the specific parameters, biological functions, rates, processes etc. that will be assessed by specific methods.

The specific objectives of the study are:

Primary objective:

To evaluate the rates of treatment failure (see definition below) in neonates and children with severe pneumonia and hypoxaemia treated by bubble-CPAP, humidified high flow (2 litres per kg per min) air / O₂ mix by nasal cannula, and standard treatment using only oxygen (0.5 – 2 litres per min) via nasal cannula.

Secondary objectives:

To evaluate complication rates, such as mortality rate at hospital discharge, rate of need for mechanical ventilation, rates of nosocomial infections (new infection occurs at least 48 hours after admission or at least 48 hours after complete resolution of treated infection at hospital and new infection will be featured with newly appeared clinical signs), rates of multi-organ failure (more than one organ failure such as renal failure and respiratory failure in addition to clinical evidence of septic shock), length of hospital stay, and rate of absconding among neonates and children with severe pneumonia and hypoxaemia when managed by bubble-CPAP, compared to high-flow, humidified oxy-therapy and standard low flow oxygen therapy.

Background of the Project including Preliminary Observations

Provide relevant background of the proposed study, and discuss the previous works on the research topic by citing specific references. Describe in a logical way how the present hypothesis is supported by the relevant background observations including any preliminary results that may be available. Provide scientific validity of the hypothesis on the basis of background information. Critically analyze available knowledge in the field of the proposed study and discuss the questions and gaps in the knowledge that need to be fulfilled to achieve the proposed goals. If there is no sufficient information on the subject, indicate the need to develop new knowledge. Also include the significance and rationale of the proposed work by specifically discussing how these accomplishments will bring benefit to human health in relation to biomedical, social, and environmental perspectives.

Despite the availability of basic care, including appropriate antimicrobial therapy and oxygen therapy, case fatality rates (CFR) for childhood pneumonia, especially among severely malnourished, remain high in developing countries(5). While CFR in severe pneumonia in well nourished children can be as low as 3-5% with good quality care (7), it can be as high as 20% or even greater in hypoxic, severely malnourished children (8). The causes of this differential CFR is multifactorial and includes different bacterial epidemiology, co-existent disease (such as diarrhoea and dehydration) and muscle weakness leading to respiratory failure (5, 6). In the management of hypoxaemia in such children standard oxygen therapy alone might not be adequate. Continuous Positive Airway Pressure (CPAP) may improve survival rates by provide additional respiratory support (9). Among premature newborns in developing countries, low birth weight and sepsis associated with hypoxaemia, apnoea and respiratory failure are common complications and are associated with high CFR (10-12). By supporting respiration and reducing the need for high concentration oxygen, CPAP might also reduce the risk of retinopathy due to oxygen toxicity (13).

The provision for advanced, high-end respiratory support, associated with high cost, is difficult to establish and not a priority in resource-poor settings where infectious diseases including pneumonia remains the leading cause of death. Equipment costs, training, and higher salaries of ICU staff are among major constrains in establishing such facilities, where funding for Western style intensive care would better be spent on public health initiatives or improving basic quality of care. In industrialized countries mechanical ventilation remains the cornerstone of intensive care, which is frequently associated with high mortality from complications (e.g. procedural errors, nosocomial infections, inadequate monitoring, late initiation of ventilation) in developing countries (1). Setting up of an appropriate, low technology-and low-cost model of referral-level intensive care is necessary in developing countries.

In the industrialized countries, CPAP is now a common form of support for patients with respiratory distress admitted to ICU units (1). It works by maintaining a positive pressure in the airway during spontaneous breathing, results in opening of the collapsed alveoli, lessening intrapulmonary shunts, and increasing functional residual capacity, which helps correct

hypoxaemia and may reduce the number of children requiring endo-tracheal intubation and mechanical ventilation (14). CPAP is most frequently delivered to neonates using conventional mechanical ventilators, which is associated with higher costs. There are other ways of delivering CPAP, such as Bubble-CPAP, which requires a source of gas flow (typically 6–8 L per minute for a neonate), an air-oxygen blender, a humidifier and a T-piece, and its expiratory arm is dipped into a bottle of water (3). The CPAP can be delivered either by helmet or facial masks or nasal canulas, and level delivered is equivalent to the length of the expiratory tube in water. NCPAP delivered by helmet has been reported to improve oxygenation better than that of facial musks and nasal canulas in young infants and older children (15). Robust equipment is currently available at a fraction of the cost of mechanical ventilators. Bubble-CPAP has several potential advantages over mechanical ventilation, such as lower cost, application by nursing staff and lower risk of complications, and has been proposed as an inexpensive and feasible method of delivering CPAP in developing countries (3).

High flow O₂ supplementation, such as using Bubble-CPAP, is useful in reduce the need for mechanical ventilation (4). However, there is no randomized study to compare the efficacy of mechanical with Bubble-CPAP or with delivery of O₂ by nasal prongs.

Nearly half of the patients admitted to the ICU of the Dhaka Hospital of ICDDR,B present with hypoxaemia, and many of them with impending respiratory failure. Children with pneumonia seen at this facility almost invariably have severe malnutrition ([name], MMed thesis, unpublished data). At this unit, children with pneumonia and hypoxaemia are initially managed with O₂ supplementation. Introduction of Bubble-CPAP at this hospital might help improve respiratory functions of greater proportion of children without the use of mechanical ventilation and thereby reduce its complications, and reduce hospital costs and mortality (14).

The main purpose of our proposed study is to compare the efficacy of (a) bubble CPAP with that of (b) the standard O₂ supplementation by nasal prongs and (c) humidified high flow nasal cannula in the management of hypoxic children with respiratory failure admitted to the ICU of the Dhaka Hospital of ICDDR,B.

Research Design and Methods

Describe in detail the methods and procedures to be used in accomplishing the objectives and specific aims of the project. Discuss the alternative methods that are available and justify the use of the method proposed in the study. Justify the scientific validity of the methodological approach (biomedical, social, or environmental) as an investigation tool to achieve the specific aims. Discuss the limitations and difficulties of the proposed procedures and sufficiently justify the use of them. Discuss the ethical issues related to biomedical and social research for employing special procedures, such as invasive procedures in sick children, use of isotopes or any other hazardous materials, or social questionnaires relating to individual privacy. Point out safety procedures to be observed for protection of individuals during any situations or materials that may be injurious to human health. The methodology section should be sufficiently descriptive to allow the reviewers to make valid and unambiguous assessment of the project.

1. Design and Methods

1.1 Study design: This will be a randomised, controlled study in which we will prospectively provide intervention in children under the age of 5 years admitted to the Dhaka Hospital of ICDDR,B and fulfilling the inclusion criteria (January 2011 and December 2012), subject to the obtaining written informed consent from respective parents/care-givers.

1.2 Eligibility Criteria

- 1.2.1** Inclusion criteria: Children of either sex, aged 0-4 years, with severe/very severe pneumonia (per WHO guidelines) and hypoxaemia ($SpO_2 < 90\%$) will be included in our study in the ARI Unit of the Longer Stay Ward (LSW), High Dependency Unit HDU, and ICU unit of Dhaka Hospital of ICDDR,B.
- 1.2.2** Exclusion criteria: Children with uncorrected cyanotic CHD, hypercapnoea ($PCO_2 > 60\text{mm of Hg}$), status asthmaticus and upper-airway obstruction, preterm baby (but not ex-preterm), and those for whom informed consent can't be secured from their parents/care-givers. Children with features (any two of three criteria given below) of "clinical failure" on admission (before enrolment into the study) will also be excluded from the study. Arterial blood gas analysis will be performed to check the exclusion criteria.

1.3 Intervention and comparators

Children under five admitted to the SCU of ICDDR, B with pneumonia and hypoxaemia will be studied. This study will evaluate the proportions of deaths in children under five in three treatment arms.

We will use sealed envelopes to randomly assign the children to one of three treatment arms. In first arm, children will receive bubble CPAP (bubble CPAP pressure of 5 to 10 cm of H₂O); in 2nd arm, children will receive standard O₂ supplementation by nasal cannula at 0.5 – 2 L/min (or 4l/min for children > 2 years); in the 3rd arm, children will receive humidified high flow air / O₂ mix at 2 L/kg/min (maximum 12L/min) through nasal cannula from a high flow generator. The three arms will be compared for rates of treatment failure (see below).

During the study period, children (whether under ventilation or not) in all three study arms will also receive standardized hospital management for pneumonia and malnutrition.

"Treatment failure" will be standardized, based on clinical and monitoring data.

During the study period any child from either study group who develops the features of "clinical failure" (any two of three criteria in the definition below) will be managed according to best practice in the clinical context. If children fail the arm of standard 2L nasal cannula O₂ they should be rescued with B-CPAP or humidified high flow air / O₂ mix at 2 l/kg/min through nasal cannula after further randomization. However, if children fail the arms of humidified high flow air / O₂ mix at 2 l/kg/min or bubble CPAP, they will receive mechanical ventilation. "Clinical failure" is the criteria to be followed to decide intubation and mechanical ventilation.

Laboratory investigations:

Routine: Blood (5.0 ml) for total and differential count of white blood cell (WBC), haematocrit, culture and sensitivity, serum electrolytes and creatinine, stool culture and urine culture, chest radiograph (CXR) on admission. Venipuncture for blood culture collection was performed by the attending physician under aseptic precautions. The puncture site was disinfected using two agents (10% povidone iodine followed by 70% rectified spirit) and left to dry for 30 to 60 seconds. 2.0 mL of blood was collected and injected into standard pediatric blood culture bottles and sent to our icddr,b microbiology laboratory where it used to be processed for the culture and sensitivity following standard procedure.

Protocol-specific: Arterial blood gas analysis, tuberculin skin test (TST), gastric lavage for acid fast bacilli (AFB) and culture for MTB.

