Patients attending this hospital are first assessed by an experienced triage nurse, which include assessment of the type of diarrhoea and degree of dehydration, and presence of other health problems including ALRI/ pneumonia, severe malnutrition, impaired mental status (convulsion), and sepsis. They redirect non-diarrhoeal patients to other appropriate city hospitals in the city. Based on assessment of diarrhoeal patients, those with uncomplicated illness without signs of dehydration are referred to the Out Patient Unit for 1-2 hours of observation, maintenance of hydration using ORS solution, and for provision of health education to the mothers/caregivers. Those with some and severe dehydration but without any associated health problems are admitted to Short Stay Ward (SSW) for correction of dehydration and maintenance of hydration using ORS and/or intravenous fluids, provision of antimicrobial therapy as appropriate, with an average stay of 24 hours. Those with associated complications of diarrhoea and/or associated health problems are referred to a physician for assessing the need for admission to either the Longer Stay Ward (LSW) or Acute Respiratory Ward (ARI) or to the Special Care Word (SCU) depending on the clinical severity. The usual associated conditions include difficult respiration, cyanosis, apnoea, hypothermia or hyperthermia, marked lethargy or comatose condition, poor peripheral perfusion not attributable to severe dehydration. Those hospitalised in SSW for 120 hours are assessed by hospital clinicians for possible admission to LSW and further workup and management. After admission to the LSW/ARI/SCU the attending physician obtained medical history, performs thorough clinical examination, makes a problem list including differential diagnoses for each of them, arranges for required laboratory workups, and develops the treatment plan following standard guidelines of the hospital. They also perform bedside procedures such as sampling blood, performing lumbar puncture etc. Oxygen saturation is determined by pulse oximeter when necessary, and blood glucose estimated by bedside Glucocheck machine in nearly all patients admitted to the LSW/ARI /SCU.

Respiratory ward Infrastructure:

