Questionnaires will be visually scanned soon after interview and marked for omissions, inconsistencies or mistakes that will be addressed immediately. Data will be entered into a personal computer using Statistical Package for Social Sciences, version 12.0 Windows, (SPSS, Chicago, IL) after creating a template for each data entry file with appropriate logical and consistency

checks. Data will be continuously entered as it is being generated in hospital, laboratory, and field. All data will be entered a second time, then consistency between two will be verified by matching with detected errors then necessary corrections will be made. In addition, data will be validated by a series of logical and range checks, producing summary statistics and tables. Data will be immediately copied on the hard disks of two computers as soon as data verification is complete.

Data analysis will be performed using the SPSS, version 12.0 Windows, (SPSS, Chicago, IL) and Epi Info (version 6.0, USD, Stone Mountain, GA). Data will be summarized and findings of one site will be compared with that of other sites(s). Statistical analyses will include descriptive as well as analytical methods. When the variable of interest is a categorical variable, the significance of differences will be evaluated by chi-square test or Fisher exact test. When the main outcome measures are continuous variables, the statistical significance of two groups (bubble CPAP vs. standard low flow or humidified high flow) will be determined by students “t” test or Mann-Whitney test as appropriate. A probability of less than 0.05 will be considered statistically significant except primary outcome (probability of less than 0.03 will be considered statistically significant for primary outcome). Strength of association will be determined by calculating odds ratio (OR) and 95% confidence intervals (CI). Finally, regression analyses will be performed for more definitive conclusions where treatment failure will be the dependent variable and factors associated with treatment failure by univariate analysis will be independent variables. Regression analyses will also be performed to evaluate independent predictors for death where deaths will be the dependent variable and factors associated with deaths in our study population by univariate analysis will be independent variables.

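### Entry SpO2 is known for every child but has no pre-specified role: treatment failure is tested unadjusted, and the regression that follows picks its covariates from the data

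*Protocol*

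**What the plan says.** **Allocation.** Section 1.3 states: "We will use sealed envelopes to randomly assign the children to one of three treatment arms". It mentions no stratification or blocking.

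**Analysis.** For categorical variables, Data Analysis says that "the significance of differences will be evaluated by chi-square test or Fisher exact test". The 0.03 level is attached to the primary outcome. The same section then plans a regression with treatment failure as the dependent variable, meant to give the firmer conclusions. Its independent variables are the factors found to be associated with failure in univariate analysis. No term is fixed in advance.

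**What is known at entry.** Section 1.2.1 requires SpO2 below 90%, so entry SpO2 exists for every child. Section 1.5 uses SpO2 below 85%, after more than half an hour on study treatment, as one of three clinical failure criteria.

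**Where children are enrolled.** Section 1.2.1 recruits "in the ARI Unit of the Longer Stay Ward (LSW), High Dependency Unit HDU, and ICU unit of Dhaka Hospital of ICDDR,B". Section 1.3 says: "Children under five admitted to the SCU of ICDDR, B with pneumonia and hypoxaemia will be studied". The statement of purpose just before Research Design and Methods names the ICU. Facilities Available describes referral to the Longer Stay Ward, "Acute Respiratory Ward (ARI) or to the Special Care Word (SCU) depending on the clinical severity".

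**The concern.** Entry SpO2 is a plausible predictor of treatment failure: it is an earlier reading of a quantity that enters the outcome definition. An analysis that ignores a known predictor leaves its contribution in the error term and gives up precision that is available without further recruitment.

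The planned regression does not close the gap. Covariates chosen by their association with the outcome in the trial's own data cannot be named beforehand. The adjusted estimate then depends on which factors pass the screen, and SpO2 may or may not be among them. The Protocol also leaves two analyses of the primary outcome side by side. The 0.03 level belongs to the outcome and is not assigned to either analysis, while the wording gives the data-driven one the greater authority.

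At stake are a modest amount of power and the credibility of the answer if the arms differ visibly in severity at entry. The validity of the trial is not at stake.

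**Working it through.** **1. The Protocol's own figure.** Inputs from section 2: failure 30% v 18%, power 90%, type 1 error 0.03, factor 11.9.

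- Two-sided factor: (z at 0.985 + z at 0.90)² = 11.91, which agrees with 11.9.
- n = (0.30×0.70 + 0.18×0.82) / 0.12² × 11.9 = 0.3576 / 0.0144 × 11.9 = 295.5. The stated 295 reproduces.
- Unadjusted power, pooled variance under the null: 89.5% at 295 per arm and 92.3% at 325.

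The sample size therefore delivers its planned power, to within rounding, without any adjustment.

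**2. What adjustment would add.** The documents give no failure rate by SpO2 band or ward, so the rates below are assumptions. The arithmetic depends only on each stratum's share of children (w) and its failure rates, and is the same whichever severity factor defines the strata. Control rates average 30%. A common odds ratio is chosen so that the bubble CPAP rates average 18%.

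Power of the Cochran-Mantel-Haenszel test at n per arm = Φ[(D − 2.170 √V0) / √V1], where

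- D = n × 0.12 / 2
- V0 = n Σ w p̄(1 − p̄) / 2, with p̄ the mean of the two arms' rates in a stratum
- V1 = n Σ w [pc(1 − pc) + pt(1 − pt)] / 4

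Worked case: two equal strata, control 10% and 50%, treated 4.8% and 31.2%, n = 295.

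- D = 17.7; V0 = 22.84; V1 = 22.14
- (17.7 − 2.170×4.779) / 4.705 = 1.56, so power is 94.0%
- Variance ratio = 0.3002 / 0.3576 = 0.839, and 0.839 × 295 ≈ 248

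| Shares | Control failure | Variance ratio | Equivalent n per arm | Power at 295 | Power at 147 |
|---|---|---|---|---|---|
| unadjusted | 30% | 1 | 295 | 89.5% | 59.5% |
| thirds | 20/30/40% | 0.972 | 287 | 90.4% | 60.8% |
| halves | 20/40% | 0.959 | 283 | 90.8% | 61.4% |
| thirds | 10/30/50% | 0.891 | 263 | 92.7% | 64.7% |
| 25/25/50% | 60/30/15% | 0.854 | 252 | 93.7% | 66.8% |
| halves | 10/50% | 0.839 | 248 | 94.0% | 67.4% |

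The gain at 295 per arm is 0.9 to 4.5 points, or 8 to 47 children per arm. The 147 column assumes a half-way look; the Protocol gives no timing.

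**3. Does chance imbalance make the unadjusted test wrong?** Under simple randomisation, the SD that stratum mix adds to an arm difference is √[2 Σ w (pc − 0.30)² / n]. Across the same cases:

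| n per arm | SD from imbalance (points) | Total SE, √(2×0.30×0.70/n) (points) |
|---|---|---|
| 295 | 0.7 to 1.7 | 3.8 |
| 147 | 0.9 to 2.3 | 5.4 |
| 75 | 1.3 to 3.3 | 7.5 |

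The imbalance is already part of the total SE. Simulated type 1 error of the unadjusted test (40,000 runs; rates 20/30/40% and 10/30/50%) was 0.029 to 0.031 at nominal 0.03.

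**4. Stratified allocation with an unstratified test.** The same simulation gave about 0.019 to 0.021 with 10/30/50% and 0.027 to 0.029 with 20/30/40%. The test becomes conservative, so allocation and analysis have to change together.

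**The case against.** **An adjusted analysis is already planned, and the choice of test can be left to a SAP.** In part this is right. SpO2 and ward could enter the regression, and silence on adjustment would be no fault in a protocol. Here, however, the Protocol names the test and fixes a covariate rule driven by the outcome data. That rule is what needs changing.

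**The gain is small and assumed.** This stands. In the mildest case it is under one point of power, and the planned power is met without it.

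**Entry SpO2 may separate children less than it seems.** Those with any two of the three clinical failure criteria "on admission (before enrolment into the study) will also be excluded from the study". A child entering below 85% therefore qualifies only without severe respiratory distress, while one entering at 88% may have it; each is then one criterion away. The band below 85% may also be small. This argues for modest expectations and against crossing SpO2 with ward in several envelope series. It does not argue against a pre-specified SpO2 term.

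**A reader might infer that wards of very different severity are being mixed.** The documents do not support this. Facilities Available ties placement to severity, but it does not mention the HDU or ICU in that triage and gives no outcome by ward. The sections also disagree on where children are enrolled; if only one unit recruits, ward has no variation to adjust for.

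**A reader might infer that allocation is known to be unstratified.** The Protocol states no strata, but it does not rule them out.

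**Conclusion.** The point holds as a modest efficiency and credibility improvement. The Protocol gives a known baseline severity measure no pre-specified role and relies on outcome-driven covariate selection for its adjusted result. The gain is about 1 to 4.5 points of power at 295 per arm. It rests entirely on assumed differences in failure rate between severity strata and on a common odds ratio across them.

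Two stronger readings should be resisted. One is that the unadjusted comparison is biased or invalid: at a single look its error rate is close to 0.03. The other is that chance imbalance in severity is what endangers a result stopped early. Imbalance is larger when arms are small, but so is the standard error that contains it. The weakness of the early-stopping provision in Data Analysis is that it gives neither timing nor boundary. That is a separate problem, and adjustment does not repair it.

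**What to change.** In Data Analysis:

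- State that the primary bubble CPAP comparisons for treatment failure, at the 0.03 level, are adjusted for entry SpO2. Either a Cochran-Mantel-Haenszel test on SpO2 bands fixed in advance, or a regression with SpO2 as a fixed term, would serve. A continuous term avoids a thin band.
- Report an adjusted risk difference or risk ratio. An adjusted odds ratio changes meaning with the covariates: in the cases above, a marginal odds ratio of (0.18/0.82)/(0.30/0.70) = 0.51 corresponds to within-stratum values of 0.45 to 0.50.
- Add enrolling unit as a second fixed factor once the statement of purpose and sections 1.2.1 and 1.3 have been reconciled on which wards recruit.
- Keep the univariate-selected regression as exploratory only.

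This costs nothing in recruitment or data collection. It must be settled before outcome data by arm are seen.

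Optionally, if envelopes are not yet prepared, block the allocation in section 1.3 within one simple severity factor and stratify the analysis on that same factor. The cost is more than one envelope series and a small risk of drawing from the wrong one. If envelopes already exist, the analysis change alone is enough.
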